## 8.2 Derivation Rules

Separate analysis dataset specifications will provide full details on all data derivations and transformations. The following sections provide a general description of the derived variables for data analyses.

### 8.2.1 Reference Dates

Reference dates are used to assign study periods relative to treatment.

- Because age is an eligibility requirement, the reference date for age will be the date of informed consent;
- Reference date for time since PID diagnosis will be the informed consent date;
- The safety reference date will be the treatment start date, and will be used to calculate study day for safety measures;
- The efficacy reference date will also be the treatment start date as the study is not randomized.

### 8.2.2 Study Day for Efficacy and Safety Measures

If the date of interest occurs on or after the reference date then the study day will be calculated as (date of interest - reference date) + 1. If the date of interest occurs before the

reference date then the study day will be calculated as (date of interest –reference date). There will be no study day 0.

### 8.2.3 Durations

Durations of an event (e.g., the duration of an AE) will be calculated in days as:

- event end date – event start date + 1;

Thus, there will be no duration of 0. If start and end time is available, it will also be used to calculate the duration. For AEs with missing end date, the approach as specified in Section 8.1.2 will be followed.

For elapsed time (e.g., the time since PID diagnosis) use

- event date – reference date.

Thus, an event which happens on the same date as the reference date will have an elapsed time of 0.

To transform durations in days into months, divide the number of days by 30.4375; to report in weeks divide the number of days by 7; to report in years divide the number of days by 365.25. These algorithms return decimal numbers, and ignore the actual calendar days in the months or years between start date and end date.

Age will be calculated as the number of complete years between a subject's birth date and the date of informed consent. If the birth date is incomplete, the subject's birth year will be used to calculate age.

### 8.2.4 Baseline Definition

Baseline data is defined as the most recent, non-missing value prior to or on the first study treatment dose date.

### 8.2.5 Change from Baseline

Change from baseline will be calculated as:

- visit value – baseline value

If either the baseline or visit value is missing, the change from baseline will be missing as well.

#### 8.2.6 Multiple Assessments

All data will be reported according to the nominal visit date for which it was reported (that is, no visit windows will be applied during dataset creation and the visit will not be re-allocated if the actual visit date deviates from the planned date according to the visit schedule in the protocol). If multiple assessments for the same visit occur, it will be distinguished why this is the case. If a laboratory sample was repeated due to technical problems the results from the valid sample(s) for this visit – the non-missing results – will be used in the analysis. If a laboratory sample was repeated as safety follow-up to monitor abnormal values of the initial sample, the initial sample (revealing the abnormal values) of this visit will be used in the analysis.

Data from all assessments (scheduled and unscheduled), including multiple assessments, will be included in listings.

#### 8.2.7 Actual Treatment

All subjects will receive the same study treatment (IgPro20) in individual doses. This is an open-label non-randomized study in which the actual treatment will be identical to the assigned treatment.

#### 8.2.8 Derived Variables

##### **Derivation of BMI**

BMI will be calculated using the following formula:

$$\text{BMI (kg/m}^2\text{)} = \text{Weight (kg)} / [\text{Height (m)}]^2.$$

##### **Derivation of flow rate per injection site**

For the Pump-Assisted Cohort the pump flow rate is to be recorded in the eDiary. The flow rate per injection site will be calculated depending on the catheter type used for injection:

Type of catheter used	Flow rate per injection site
Straight	= Pump flow rate (mL/h)
Bifurcated	= Pump flow rate (mL/h) / 2
Trifurcated	= Pump flow rate (mL/h) / 3
Quadrifurcated	= Pump flow rate (mL/h) / 4

For the purposes of this study, equal flow rate in every catheter branch will be assumed.

#### Derivation of infusion volume per injection site

The infusion volume per injection site will be calculated based on the infusion volume administered via a specific pump depending on the catheter type used for injection:

Type of catheter used	Volume per injection site
Straight	= Pump volume (mL)
Bifurcated	= Pump volume (mL) / 2
Trifurcated	= Pump volume (mL) / 3
Quadrifurcated	= Pump volume (mL) / 4

For the purposes of this study, equal distribution of total volume into every catheter branch will be assumed.

#### 8.2.9 Subgroups

The study design does not include any stratification factors, and there are no plans for post hoc stratification. There are no formal plans for investigating any covariates.

The analysis of infusion parameters will be presented stratified by

- Age class ( $\leq 17$  years,  $> 17$  years);
- BMI class ( $< 30$  kg/m^2,  $\geq 30$  kg/m^2).

It will be specified in the respective sections which tables will be affected.

### **8.3 Study Periods Relative to Treatment**

Not applicable.

### **8.4 Values of Potential Clinical Importance**

Not applicable.

## **9 Study Population**

Unless otherwise stated, tables will be based on the SAF. Listings will usually show all data available (i.e. based on the ScAS); listing for derived variables may be based on a particular analysis set which will be specified in the corresponding section. Summaries and data listings will use labels as specified in Section 7.2.

### **9.1 Disposition of Subjects**

A summary table based on the ScAS will be provided by cohort and Total showing the number of subjects with the following information:

- Number of subjects screened;
- Number of screening failures and reason for screening failure;
- Number of subjects enrolled into the study;
- Number of subjects who entered each infusion parameter level;
- Number of subjects who completed the study;
- Number of subjects who discontinued from the study prematurely with reason for discontinuation;
- Infusion parameter level at which subjects discontinued from the study.

Reasons for study discontinuation will be presented in descending order of their frequency.

A by-subject listing for all available data with the information as described in Section 7 as well as screening status, reason for screening failure (in- or exclusion criterion numbers), date of enrollment, date of informed consent, date of eligibility, date of first and last treatment, maximum tolerated infusion parameter level, date of study completion or discontinuation, and reason for study discontinuation will be presented. Another listing for all available data will present the individual visit dates for all visits (scheduled and unscheduled) which the subject attended.

## 9.2 Protocol Deviations

In this study, the ScAS, the FAS, and the SAF are defined. Thus, protocol deviations will not have any impact on the statistical analysis of the study as no subjects will be excluded from the defined analysis sets because of protocol deviations. From a clinical perspective, there is still an interest to report protocol deviations.

A summary table by cohort and Total with the number and percentages of subjects in the analysis sets Screened, FAS, and Safety will be provided.

The following by-subject listings for all available data with the information as described in Section 7 as well as the information listed below will be provided:

- Inclusion and exclusion protocol deviations;
- Other protocol deviations.

## 9.3 Demographic and Baseline Characteristics

The following summaries will be provided for the SAF; tables will be presented by cohort and Total:

- Demographic characteristics: sex, age (years), age category, race, ethnicity, height (cm), weight (kg), and BMI ( $\text{kg}/\text{m}^2$ ) at Screening. Age, height, weight, and BMI will be summarized as continuous variables. Age and BMI will also be categorized and summarized (Age: < 18 years,  $\geq 18 - \leq 65$  years, > 65 years; 0 -  $\leq 27$  days, > 27 days - < 2 years,  $\geq 2 - < 12$  years,  $\geq 12 - < 18$  years,  $\geq 18 - \leq 65$  years, > 65 -  $\leq 84$  years, > 84 years;  $\leq 17$  years and > 17 years. BMI: <  $30 \text{ kg}/\text{m}^2$  and  $\geq 30 \text{ kg}/\text{m}^2$ );
- Disease characteristics: PID category, time since first PID diagnosis (years), historic IgG levels at diagnosis (g/L), and pre-study trough levels (g/L);

- Medical history: coded using Medical Dictionary for Regulatory Activities (MedDRA) version 20.0 or higher will be presented by System Organ Class (SOC) and Preferred Term (PT) – include medical history terms with Medical History Start Date Type “Historical Condition” as entered in the eCRF or medication end date / evidence for end date prior to or on the informed consent date;
- Concomitant diseases (by SOC and PT) will be presented along with concomitant therapies and method of contraception (by Anatomical Therapeutic Chemical [ATC] Class level 4 and unique term) – include medical history terms with Medical History Start Date Type “Concomitant Disease” as entered in the eCRF or end date / evidence for end date after the informed consent date or flagged “Ongoing” and concomitant medication terms which are flagged ongoing, have end date missing, or end date / evidence for end date after the informed consent date.

By-subject listings for all available data with the information as described in Section 7 will be provided for:

- Demographic data: sex, age (years), age group, race, ethnicity, height (cm), body weight (kg), and BMI (kg/m^2) at Screening;
- Disease characteristics: PID category, time since first PID diagnosis (years), historic IgG level at the time of diagnosis (g/L), pre-study IgG level (g/L);
- Medical history and concomitant diseases (medical history term, SOC, PT, start and end date, medical history term type);
- Reproductive system findings (childbearing potential, method of birth control, pregnancy during the study, date of pregnancy test, and pregnancy test result).

#### **9.4 Concomitant Medications**

Concomitant medications will be coded using World Health Organization Drug Dictionary Enhanced (WHO-DDE) B2 version March 2016 or more recent version. The summary of concomitant medications will show the number and percentage of subjects taking concomitant medications by ATC class and unique term. ATC Level 4 will be used for the summary tables and listing unless coding is not available at level 4. In these cases level 3 ATC name will be used. Similarly, if the level 3 ATC name is not available then the level 2 ATC name will be used and if the level 2 ATC name is not available then the level 1 ATC

name will be used. ATC Level 1 information will be included in the dataset created but will not appear in the listing or summary except when all other levels are not available.

The following classification of concomitant medication related to start date of study treatment will be applied:

- Assign to ‘Prior Only’ if the concomitant medication start date and end date is prior to study treatment start date; if the subject has not taken any study treatment; or the concomitant medication start date is missing and the concomitant medication end date is before the study treatment start date. If the concomitant medication start or end date is partially missing, the concomitant medication will only be assigned to ‘Prior Only’ if the partial dates give clear evidence that the concomitant medication stopped prior to study treatment start date;
- Assign to ‘Prior and Concomitant’ if the concomitant medication start date is prior to study treatment start date and the concomitant medication end date is on or after study treatment start date or missing (ongoing treatment). If the concomitant medication start or end date is partially missing, the concomitant medication will only be assigned to ‘Prior and Concomitant’ if the partial start date gives clear evidence that the concomitant medication started prior to study treatment start date;
- Assign to ‘Concomitant Only’ if the concomitant medication start date is on or after the study treatment start date or the concomitant medication start date is partially or completely missing and there is no clear evidence from the partial date that the concomitant medication falls into one of the other categories above.

In the summary of concomitant medications, each subject will be counted once within each unique term (Any Medication, ATC Class, and unique term). For example, if a subject takes Amoxicillin on two separate occasions, the subject will be counted only once under the medication “Amoxicillin”, once in the corresponding ATC class, and once for “Any Medication”. The number and percentages of subjects based on the SAF along with the number of reports will be presented for ‘Prior and Concomitant’ and for ‘Concomitant Only’ medications by cohort and Total.

A by-subject listing for all available data with the information as described in Section 7 as well as medication/therapy, start and end date and time or ongoing, dose, route, frequency, primary indication for the concomitant medication, AE term if applicable, medical history

term if applicable, and concomitant medication flag (Prior Only, Prior and Concomitant, Concomitant Only) will be provided.

## 10 Efficacy

CCI [REDACTED]

CCI [REDACTED]  
[REDACTED]  
[REDACTED]  
[REDACTED]

A by-subject listing for the FAS with the information as described in Section 7 CCI [REDACTED] will be provided.

(Note: details for the primary safety endpoint are described in Section 11.1).

### 10.1.1 Sensitivity Analyses

Not applicable.

### 10.1.2 Subgroup Analyses

The analysis of infusion parameters will be stratified by subgroups as specified in Section 8.2.8.

## 10.2 Treatment Compliance

Treatment compliance will be monitored by reviewing the subject's diary and counting the used vials.

### Dose and Volume Compliance from Subject's Diary:

Treatment compliance will be analyzed by comparing the actual administered dose (mg/kg) and the actual administered volume (mL) over all infusion sites to the prescribed dose (mg/kg) prior to the study and the planned volume (mL) as in the diary, respectively.

- Compliance per Infusion (%) =  $\frac{\text{actual amount per infusion}}{\text{planned amount per infusion}} * 100$ ;
- Overall Compliance (%) =  $\frac{\text{cumulative actual amount over all infusions}}{\text{cumulative planned amount over all infusion}} * 100$ ;

where amount is either the dose (mg/kg) or the volume (mL).

In the Pump-Assisted Cohorts, the compliance per infusion equals the weekly compliance as one infusion per week is scheduled. In the Manual Push Flow Rate Cohort, subject’s weekly compliance will be calculated as the mean over all infusions in the particular week.

The following summaries will be provided by cohort and infusion parameter level based on the SAF:

- Descriptive statistics for overall compliance and subject’s weekly compliance;
- Percentage overall compliance categorized by < 90%, 90% - 110%, and > 110%.

A by-subject listing for the SAF with the information as described in Section 7 as well as prescribed and actual dose per infusion, planned and actual volume per infusion, compliance for dose and volume per infusion, subject’s weekly dose compliance, and overall dose compliance will be provided.

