## 4 Study Design

### 4.1 Study Design

This multicenter, open-label, parallel-arm, non-randomized study is designed to evaluate safety and tolerability of higher infusion parameters of IgPro20 in subjects with primary immunodeficiency (PID). A target of 45 evaluable subjects (i.e., 15 subjects per cohort) is needed. Enrolled subjects will include a target of 14 (30%) pediatric subjects  $\leq 17$  years of age and a target of 9 (20%) obese subjects with body mass index (BMI) of  $\geq 30$  kg/m^2.

Pediatric and obese subjects may be distributed across any or all of the treatment cohorts without respect to balanced enrollment within the cohorts for these subpopulations..

Assignment to one of the cohorts will take place at the Screening visit and subjects cannot be

changed later to another cohort. The study will include 3 cohorts with a minimum of 15 subjects each as follows:

- Pump-Assisted Volume Cohort (weekly infusions): Volume per injection site of 25 mL up to 50 mL;
- Pump-Assisted Flow Rate Cohort (weekly infusions): Flow rate per injection site of 25 mL/hour (h) up to 100 mL/h
- Manual Push Flow Rate Cohort (2 to 7 infusions per week): Flow rate per injection site of 25 to 30 mL/h up to 120 mL/h (equivalent of approximately 0.5 mL/minute up to 2 mL/minute)

Each cohort will test 3 infusion parameter levels (for Pump-Assisted Flow Rate Cohort – 4 levels) for at least 4 weeks each over a duration of 12 weeks (for Pump-Assisted Flow Rate Cohort – 16 weeks). After the fourth week on each level, subjects may switch to the next infusion parameter level, if the current level has been tolerated (e.g., from 25 to 50 mL/h). During the study the weekly dose will remain unchanged (as prescribed by treating healthcare provider, usually within 100-200 mg/kg per week range); only the respective infusion parameter under evaluation will change. If a subject is unable to tolerate the respective infusion parameter level (i.e., is a non-responder at that level, for definition see Section 11.2), the subject will continue study participation at the individually previously tolerated infusion parameter level for the remaining full study duration, to collect safety information.

The final analysis to support the CSR will take place after all subjects have completed or terminated the study.

The schedule of assessments planned for the study can be found in the protocol.

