**Figure 1 Study Flowchart**

Subjects in the Pump-Assisted Cohorts will administer weekly treatment and subjects in the Manual Push Cohort will administer frequent infusions (i.e., 2-7 times per week). Subjects in the Manual Push Cohort should maintain the same frequency of infusions per week throughout the whole study; including one month prior to Day 1 (date of Week 1 visit at the

site). The infusion parameters not under test (e.g., volume per injection site in the Flow Rate Cohort) should not exceed the levels used before the study.

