### **Planned and Actual Times in Summaries**

Planned times for study treatment dosing will be used in all tables and summary figures.

Generally, only pre-specified planned times will be used in the summaries, statistical analyses, and calculations of any derived parameters; unscheduled assessments will be included in the listings. However, both unscheduled and scheduled assessments will be included in worst-case post-baseline shift displays for laboratory data and in any summary or listing of potential clinical importance values for vital signs.

The infusion start date and time will be mapped to study weeks in the following way: The infusions will be sorted by start date and time and will be consecutively numbered. The infusions will be mapped to study weeks using the consecutive numbers.

Study Week	Pump-Assisted Cohorts	Manual Push Flow Rate Cohort			
		Infusions Per Week			
		2	3	4	5
1	Infusion 1	Infusion 1-2	Infusion 1-3	Infusion 1-4	Infusion 1-5
2	Infusion 2	Infusion 3-4	Infusion 4-6	Infusion 5-8	Infusion 6-10
3	Infusion 3	Infusion 5-6	Infusion 7-9	Infusion 9-12	Infusion 11-15
4	Infusion 4	Infusion 7-8	Infusion 10-12	Infusion 13-16	Infusion 16-20
5	Infusion 5	Infusion 9-10	Infusion 13-15	Infusion 17-20	Infusion 21-25
...	...				
9	Infusion 9	Infusion 17-18	Infusion 25-27	Infusion 33-36	Infusion 41-45
...	...				
12	Infusion 12	Infusion 23-24	Infusion 34-36	Infusion 45-48	Infusion 56-60
...	...				
16	Infusion 16 (PAFR)				

PAFR: Pump-Assisted Flow Rate Cohort

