**Table 3: Responder requirements in Manual Push Flow Rate Cohort**

Manual push infusions per week	Total number of infusions scheduled for parameter set	Minimum number of valid infusions ( $k$ )
2	8	5
3	12	7
4	16	10
5	20	12
6	24	15
7	28	17

Rationale for number of valid infusions to qualify a responder in the Manual Push Flow Rate Cohort: The probability for a subject to be a responder for a certain infusion parameter is assumed to be 50% irrespective of the value of the infusion parameter itself, i.e. identical to the assumed response rate in Clinical Study Protocol Section 11.1. This assumption is based on the expectation that there will be no infusion-related reasons for a subject to interrupt the infusion or change the infusion parameters. To achieve  $\geq 3$  out of 4 valid infusions the probability for a single infusion to be valid has to be  $\geq 61\%$  for Pump-Assisted Cohorts. Using this 61% success probability for a single infusion in the Manual Push Flow Rate Cohort the minimum number of successes (k) in Table 3 corresponds to a probability for a subject to be a responder of at least 50%.

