### 11.3 Extent of Exposure

Actual dose in mg/kg will be taken as entered in the database. For the Manual Push Flow Rate Cohort, the planned weekly volume will be derived from the planned weekly dose as entered in the eCRF assuming the nominal IgG content of IgPro20 being 200 mg/mL:

planned volume (mL) = planned dose (mg/kg) \* body weight (kg) / 200 mg/mL.

Subject's duration of exposure (days) in each infusion parameter level will be calculated as

(minimum of (treatment end date in parameter level [i] + 7 days, treatment start date in parameter level [i+1] – 1 day, study completion date) – treatment start date in parameter level [i]) + 1.

Subject's overall duration of exposure (days) will be calculated as

study completion date – date of first treatment + 1.

Duration in weeks will be derived by dividing the above item by 7.

Descriptive statistics for duration of exposure in weeks for each infusion parameter level and overall will be presented. In addition, the subject-years of exposure for each infusion parameter level and cohort will be given.

Subject's prescribed and actual dose (mg/kg) and total planned and actual volume (mL) per week will be summarized descriptively by cohort and infusion parameter level.

Number and percentage of incomplete infusions or infusions stopped will be presented. The base for the percentage will be the total number of infusions within the cohort.

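### Weekly compliance as defined cannot fall when an infusion is skipped, because neither its formula nor its study weeks refer to the scheduled infusions

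*SAP*

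**What the plan says.** SAP Sections 2.2 and 10.2 define compliance per infusion as the actual amount divided by the planned amount of that same infusion, in percent. Two rules turn this into a weekly figure:

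- Pump cohorts: "the compliance per infusion equals the weekly compliance as one infusion per week is scheduled".
- Manual push: a subject's "weekly compliance will be calculated as the mean over all infusions in the particular week".

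Overall compliance divides the cumulative actual amount by the "cumulative planned amount over all infusion". It is also reported in three bands: below 90%, 90 to 110%, and above 110%.

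The study week comes from SAP Section 7, under Planned and Actual Times in Summaries. Infusions are ordered by start date and time and numbered in sequence, and then: "The infusions will be mapped to study weeks using the consecutive numbers". SAP Section 8.1.1 imputes a missing causality for adverse events and no other non-date data.

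SAP Section 11.3 adds that the "total planned and actual volume (mL) per week will be summarized descriptively by cohort and infusion parameter level". For manual push it derives the planned weekly volume from the planned weekly dose.

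The design fixes what should be adhered to. SAP Section 4.1: "During the study the weekly dose will remain unchanged". SAP Section 4.3: "Subjects in the Manual Push Cohort should maintain the same frequency of infusions per week".

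**The concern.** A weekly compliance figure should show whether the subject received the planned weekly amount. The plan's formula looks only at infusions that took place, and asks of each whether its own planned amount was delivered. The number of infusions scheduled in the week does not appear.

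The week assignment then closes the gap. A missed infusion has no start time and so gets no number, and the next infusion takes its place. Only a reduced amount at an infusion that was given can lower the weekly figure.

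At stake is whether the weekly table can show a departure from the constant weekly dose or from the constant manual-push frequency when that departure arises through skipped infusions. As written, it cannot.

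**Working it through.** **Inputs.** Compliance per infusion and the two weekly rules (SAP 10.2); the running-number week table (SAP 7); no imputation of amounts (SAP 8.1.1); four weeks per level (SAP 4.1); one infusion per week for pump and 2 to 7 for manual push (SAP 4.3). The patterns of missed infusions below are assumptions, since the documents give no rate. Every infusion given is taken as complete, with equal planned volumes.

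**Step 1: reproduce the week table.** At f infusions per week, week w covers running numbers (w − 1)f + 1 to wf.
- f = 3, w = 12: 34 to 36, as printed.
- f = 5, w = 5: 21 to 25, as printed.

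So mapped week = running number / f, rounded up, whatever the calendar date.

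**Step 2: pump, 3 of 4 infusions given at the first level.** The three infusions get numbers 1, 2, 3 and fill Weeks 1 to 3. The first infusion at the second level gets number 4 and fills Week 4. Each filled week shows 100%. Against schedule the level is at 3/4 = 75%.

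**Step 3: manual push, 5 per week, one miss every week for 12 weeks.** Given: 4 × 12 = 48 of 60. Numbers 1 to 45 fill Weeks 1 to 9, numbers 46 to 48 fall in Week 10, and Weeks 11 and 12 are empty. The mean over infusions is 100% in every filled week. Against schedule each calendar week is at 4/5 = 80%.

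**Step 4: is there a floor?** A pump subject who gives 1 of 4 infusions in full at a level is at 1/4 = 25% of schedule. The infusion given still scores 100%, so the formula sets no lower limit.

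**Step 5: a single miss, traced by week.** Manual push, 3 per week, the second infusion of calendar Week 2 skipped, so 35 of 36 given.

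| | Plan's rule | Calendar week, scheduled denominator |
|---|---|---|
| Week 2 | 100% | 2/3 = 66.7% |
| Other weeks | 100% each | 100% each |
| 12-week mean | 100% | 35/36 = 97.2% |

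The first infusion of each calendar week from 3 to 12 is labelled one week early, which puts 10 of the 35 infusions in the wrong week. Mapped Week 4 holds numbers 10, 11 and 12. Numbers 10 and 11 were given at the first level; number 12 is the first infusion at the second level. Mapped Week 8 is mixed in the same way.

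**Step 6: overall compliance.** In the case of Step 3, if the denominator means infusions given, the result is 48/48 = 100% (middle band). If it means infusions scheduled, it is 48/60 = 80% (below 90%). The wording allows both.

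**The case against.** **The diary may record missed infusions.** Section 10.2 compares with the prescribed dose and with the planned volume held in the diary. If the diary stored a missed infusion as a zero-amount record with a start time, it would be numbered and would lower the mean. This limit is real. But the documents provide for no such record, and the operative formulas work infusion by infusion.

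**Misses are visible elsewhere.** This stands. Vial counts (SAP 10.2), infusion counts by level (SAP 11.1), date-based exposure duration by level (SAP 11.3) and the per-infusion listings all help to reveal them. That limits the consequence; it does not make the weekly figure right.

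Four stronger readings are tempting and are not supported:

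- *Weekly dose and volume by level are distorted.* A reader might average over mapped weeks. In Step 5 the second level then has 1, 3, 3, 3, 2 infusions in Weeks 4 to 8, or 12/15 = 80%. But Section 11.3 states no such averaging rule. Dividing the same counts (11, 12, 12) by the 12 scheduled per level gives the true 91.7, 100 and 100%. No figure can be claimed.
- *The responder minimum bounds the error.* It does not; weekly compliance does not depend on responder status, as Step 4 shows.
- *Overall compliance is wrong.* It is wrong only under one reading of its denominator.
- *The primary endpoint is affected.* A responder needs a minimum number of valid infusions, and an infusion that was not given cannot count as valid. The weekly compliance figure is not used there.

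**Conclusion.** The point holds as a minor one. Applied as written, the weekly compliance rule shows 100% for any subject whose given infusions were complete, however many were skipped: against 75% of schedule for pump with 3 of 4 given, 80% for manual push at 5 per week with one miss each week, and 25% for pump with 1 of 4 given. This rests on the absence of zero-amount diary records.

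Overall compliance shares the fault only if its denominator is read as infusions given. Running-number weeks also label later infusions too early after a miss and can mix two levels in one manual-push week; what this does to the Section 11.3 summaries cannot be settled from the text.

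The established effect is limited to descriptive compliance tables. Its practical size is unknown.

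**What to change.** 1. For compliance and weekly exposure, assign the study week by infusion start date relative to the visit that began the level (Day 1 for the first level). Assign each infusion to its nearest scheduled week. Plain seven-day blocks would not do: a pump infusion on Day 14 lies within the protocol's window for Week 3 (Day 15 ± 1) but would count as a second infusion in Week 2 and leave Week 3 empty.
2. Define weekly compliance as total actual amount divided by the planned scheduled amount for that week. For manual push, use the planned weekly volume already derived in Section 11.3. Count missed scheduled infusions as zero up to study end or discontinuation.
3. Use the same scheduled denominator for overall compliance, and say so. For manual push the scheduled count per level is already tabulated in SAP Table 3, under "Total number of infusions scheduled for parameter set".

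The cost is SAP wording, the window rule and minor programming. Infusion start dates and times and the planned weekly dose are already collected. Reported compliance will be lower wherever infusions were missed.
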